## 2.2. Proof of Concept (POC) Phase 2 Study

| Objectives       | Endpoints  |
|------------------|--|
| Primary   | 
Primary Efficacy Endpoint
 
 
The proportion of patients with a SRI-4 response at Day 210
 
   |
| Secondary | 
Secondary Efficacy Endpoints
 
 
The proportion of patients with:             
 
- SRI-4 response at each visit
 
- SRI-5 and SRI-6 response at each visit
 
- a sustained reduction of oral corticosteroid (CS) (<math>\leq 7.5</math> mg/day and <math><</math> Day 0 dose) between Day 150 and Day 210
 
- new or recurrent BILAG flares (<math>\geq 1</math> qualifying BILAG A or <math>> 1</math> qualifying BILAG B) through Day 210
 
- PGA worsening
 
- a BICLA response
 
- a CLASI response
 
- medication failures
 
 
 
Change and percentage change from baseline at each visit in:             
 
- CLASI
 
- PGA
 
- Total number of swollen joints, tender joints, and active joints (swelling and tenderness in the same joint) in the ACR-28 joint count
 
- SLEDAI-2K
 
- SLICC/ACR damage index
 
 
 
TTMF
 
Group mean percent reduction in corticosteroid administration from baseline Day 0 dose through Day 210 in patients receiving <math>\geq 7.5</math> mg/day prednisone equivalent at Day 0
 
 |

Sponsor: Boston Pharmaceuticals, Inc.  
Protocol Number: BOS161721-02  
SAP Version and Date: Version 4.0, 23Apr2021

| Objectives | Endpoints  |
|------------|--|
|            | 

• Duration of longest SRI-4 response

• Time to first BILAG flare (<math>\geq 1</math> new or recurrent BILAG A or <math>> 1</math> new or recurrent BILAG B) relative to baseline through Day 210

   |

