**Evaluability/Non-Responders:**

**Medication Failures:** Patients who received prohibited medications or undergo unallowable corticosteroid (CS) usage will be considered “medication failures” and will be treated as non-responders at time points on and following the first date of prohibited medication or unallowable CS usage for the primary efficacy analysis. Prohibited medications are detailed in Appendix 4 of the study protocol. Prohibited medications and unallowable CS usage will be recorded as protocol deviations in the clinical database.

A patient is considered to have unallowable CS usage if any of the following is not met:

- A maximum daily dose of 30 mg/day of oral CS will be acceptable for eligibility for the study. For patients whose only SLE treatment is steroids, their stable steroid dose must be at least 10 mg/day and no more than 30 mg/day for a minimum of 6 weeks at time of randomization on Day 0
- Topical steroids may be used, but the dose must be stable for at least 6 weeks prior to Day 0, and be maintained at a constant dose throughout the study duration until the rashes resolve. PRN topical steroids are not permitted
- Once the patient has received the first dose of study drug (Day 0), tapering of oral steroids will be highly encouraged and should be continually evaluated during the protocol-allowed tapering windows (Day 0 through Day 150) with the target of achieving a CS daily dose of < 7.5 mg and < Day 0 dose between Day 150 and Day 210
- Between Day 150 and Day 210 (i.e., within 60 days of primary endpoint assessments), oral CS doses must be held constant
- CS Burst for SLE-related Indications
  - After Day 0 (first dose of study drug), a maximum of 1 oral CS “burst” equivalent to  $\leq$  40 mg/day prednisone for increased SLE disease activity will be allowed between Day 0 and Day 120, which must be tapered down to the baseline (Day 0) CS dose or lower within 14 days of initiation of the “burst”. Any “burst” continuing after Day 120 or occurring after Day 120 is considered a protocol deviation.
  - Alternatively, a single intramuscular (IM) dose of methylprednisolone ( $< 40$  mg) is permitted during this period.
- CS Burst for Non-SLE-related Indications
  - A single treatment of oral prednisone equivalent of  $\leq$  40 mg/day for 14 days is permitted for a non-SLE indication, though it must be completed prior to Day 120. No long acting steroid injections are permitted.

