#### 7.2.4.3. Percent Reduction in CS Administration from Day 0 through Day 210 (POC)

The percent reduction in CS administration from Day 0 through Day 210 determined based on the average daily CS usage will be summarized for POC Phase 2 by treatment group and visit. Average daily dose will be calculated for nominal visits as defined in Section 7.2.4. This will be performed for patients in the FAS who received  $\geq 7.5$  mg/day prednisone equivalent at Day 0. Patients considered medication failures will be excluded from the percent reduction analysis at timepoints on and after the first date of medication failure.

#### 7.2.5. Proportion of new or recurrent BILAG A flare or $>1$ BILAG B flare through Day 210

The proportion of patients with a new or recurrent BILAG A flare or  $>1$  BILAG B flares through Day 210 will be summarized by study phase and treatment group in the FAS. Statistical methods described in Section 7.1.1 will be implemented. BILAG flares will be adjudicated, recorded in the clinical database, and summarized as recorded in the clinical database. Flare assessments will be performed on BILAG grades whether or not designation of a BILAG grade required carrying component data forward by the assessor. However, no LOCF methods will be implemented with respect to flare data itself. When discrepancies between the two-reviewers occurs, the adjudicated flare determination will be used for analyses. The proportion of new or recurrent BILAG A flare or  $>1$  BILAG B flare will be summarized overall and by nominal visit. The denominator for percentages of patients with a new or recurrent flare will be patients in the FAS with a post-baseline BILAG assessment at the given visit.

Statistical testing data will be omitted from MAD Phase 1b treatment group displays.

Sponsor: Boston Pharmaceuticals, Inc.  
Protocol Number: BOS161721-02  
SAP Version and Date: Version 4.0, 23Apr2021

Results as recorded in the clinical database will be presented in separate data listings for BILAG SLE history, BILAG-2004 index, and BILAG grading for all randomized patients.

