#### 7.2.13. Duration of Longest SRI-4 Response

Duration of longest SRI-4 response will be computed for patients who have been identified as a responder at least once based on criteria defined in Section 7.1.1 utilizing LOCF methods consistent with the primary efficacy analysis. The duration of longest response will be defined as the longest period a patient meets the SRI-4 responder criteria at consecutive visits. This will be computed as the date of last consecutive SRI-4 response – date of first consecutive response + 1. If the last consecutive response is based on LOCF methods and the last consecutive response does not have a date, duration of longest SRI-4 Response will be computed as the (date of last non-missing consecutive SRI-4 response + 30) – date of first consecutive response + 1.

The duration of longest SRI-4 response will be analyzed using an analysis of variance (ANOVA) model with treatment group as the effect. The p-value for the difference between the BOS161721 and placebo group is based on the F-test.

The mean, SD, median, minimum, maximum, Q3, Q4, LS Mean estimate, its standard error and 90% CI will be tabulated by treatment group and for the difference between treatment groups (BOS161721 versus placebo).

If a patient has missed a visit between two scheduled visits with a response at both, the patient will be counted as having a response at the missed visit unless otherwise specified.

Duration of longest SRI-4 response will be displayed in the SRI response listing.

These analyses will also be performed for the MAD Phase 1b with the exception of the statistical testing.

#### 7.2.14. Time to First BILAG A Flare or >1 BILAG B Flare through Day 210

Time to first BILAG A Flare or >1 BILAG B Flare will be computed as the event date (as described below) – randomization date + 1. If a patient is designated as a medication failure prior to or on their day 210 visit, they will be considered as having a BILAG flare (event) as of the date of first dose of the medication leading to the medication failure designation due to prohibited medication or unallowable CS burst.

Time to first BILAG A Flare or >1 BILAG B Flare will be analyzed with Kaplan-Meier methods described for TTMF and censoring as described in Table 5. Kaplan-Meier curves will be plotted over time.

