**Table 5**

| Situation   | Date of Event or Censoring   | Outcome |
|--|---|----------------|
| Patient has a BILAG A Flare or >1 BILAG B Flare (Noted as BILAG 1A/2B Flare) prior to or on their Day 210 visit                  | Date of first BILAG 1A/2B Flare   | Event          |
| Patient is designated a medication failure (received prohibited meds or unallowable CS burst) prior to or on their Day 210 visit | Date of first dose of medication leading to medication failure designation. These dates will be obtained from date of the medication failure identified by the sponsor based on the prior and concomitant medication eCRF form. | Event          |
| Patient withdraws from study (no BILAG 1A/2B Flare, no medication failure) prior to or on their Day 210 visit                    | Censored at date of last non-missing BILAG flare assessment (prior to or on withdrawal) through Day 210   | Censored       |
| Patient completes the study (no BILAG 1A/2B Flare, no medication failure)  | Censored at date of last non-missing BILAG flare assessment through Day 210   | Censored       |
| Patient dies during study (no BILAG 1A/2B Flare, no medication failure) prior to or on their Day 210 visit                       | Censored at the day of death  | Censored       |

An event will be counted once in a patient who is a medication failure and also experiences a BILAG flare. Date of event will be the date of the earlier of the two reasons.

These analyses will also be performed for the MAD Phase 1b with the exception of the statistical testing.

Time to first BILAG A Flare or >1 BILAG B Flare data will be provided in a by-patient listing in the full analysis set.

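### The analysis titled time to first BILAG flare also counts medication failures as flares, although Section 2.2 and the flare proportion in Section 7.2.5 are defined by BILAG flare alone

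*SAP*

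**What the plan says.** All references are to SAP version 4.0.

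- **Section 2.2 (Phase 2 objectives and endpoints)** lists two secondary flare endpoints: the proportion of patients with "new or recurrent BILAG flares" and "Time to first BILAG flare". Both are defined as at least one BILAG A or more than one BILAG B through Day 210. Neither mentions medication failure.
- **Section 7.2.5 (flare proportion)** states: "BILAG flares will be adjudicated, recorded in the clinical database, and summarized as recorded in the clinical database". The denominator "will be patients in the FAS with a post-baseline BILAG assessment at the given visit". It contains no medication-failure rule.
- **Section 7.2.14 and Table 5 (time to first flare)** add a second kind of event. For a patient designated a medication failure by the Day 210 visit, "they will be considered as having a BILAG flare (event) as of the date of first dose of the medication" that led to the designation. Both places gloss the cause as prohibited medication or an unallowable corticosteroid burst. The note under Table 5 adds: "An event will be counted once in a patient who is a medication failure and also experiences a BILAG flare", dated at the earlier of the two.
- **Section 7.2.12.2 and Table 4** already give medication failure its own Kaplan-Meier curve, log-rank test and hazard ratio. Section 7.2.14 borrows the same methods.

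**The concern.** Two endpoints share one event definition in Section 2.2 but are scored by different rules in Section 7. Medication failure is not a BILAG outcome. Under Section 7.1.1 it includes any prohibited medication, intra-articular or intravenous steroid, and steroid use for non-lupus indications outside the stated allowance.

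A hazard ratio labelled as flare thus mixes disease activity with medication use. If failures differ between arms, the difference enters the flare result. The same failures through Day 210 also feed the time-to-medication-failure test, and Section 4.3 makes no multiplicity adjustment. One difference in medication use could then read as two separate benefits. If failures are balanced, they dilute a real flare effect. The SAP does not explain the difference in scoring, and it plans neither a flare-only time-to-event analysis nor a composite proportion.

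**Working it through.** **Does Section 7.2.5 import the failure rule indirectly?** It says "Statistical methods described in Section 7.1.1 will be implemented". Three features show that this means the test and confidence interval, not the failure rule:

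1. Section 7.2.6.1 (PGA worsening) uses the same phrase and then separately cites Table 2 to bring in the primary-analysis handling of failures.
2. Section 7.2.12.1 uses the phrase for the medication-failure endpoint itself, where importing the rule would be circular.
3. Where the SAP wants the rule in a secondary endpoint, it says so: sustained steroid reduction (7.2.4.2), percent steroid reduction (7.2.4.3) and item 5 of the BICLA definition (7.2.7).

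Scoring flares as recorded in the database also leaves no room for imputed ones. The two rules therefore differ.

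**Size.** The plan gives no flare or failure rate and no power statement for these endpoints, so there is no figure to reproduce. Arm sizes follow from Section 3.3: 96 evaluable patients at 2:1 gives 96 × 2/3 = 64 and 96 × 1/3 = 32. The level is two-sided 0.10. All counts below are assumptions, and *failure-only* means a medication failure without a flare.

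The test is Pearson's, uncorrected: z = (p₁ − p₀) / √[p̄(1 − p̄)(1/64 + 1/32)], where 1/64 + 1/32 = 0.046875. As a guide to the hazard ratio, under proportional hazards with everyone followed to Day 210, HR = ln(1 − p₁)/ln(1 − p₀).

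*Equal flares, unequal failures*
- Flares only: 16/64 = 25.0% versus 8/32 = 25.0%. Difference 0, p = 1.00, HR = 1.00.
- Add 4 and 8 failure-only patients: 20/64 = 31.3% versus 16/32 = 50.0%. p̄ = 36/96 = 0.375; SE = √(0.375 × 0.625 × 0.046875) = 0.1048; z = −0.1875/0.1048 = −1.79; p = 0.074. HR = ln(0.6875)/ln(0.5) = 0.54.

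*The same failures, half of them in patients who also flare.* Failure-only counts fall to 2 and 4: 18/64 = 28.1% versus 12/32 = 37.5%. p̄ = 30/96 = 0.3125; SE = √(0.3125 × 0.6875 × 0.046875) = 0.1004; z = −0.0938/0.1004 = −0.93; p = 0.35. HR = ln(0.71875)/ln(0.625) = 0.70.

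*Real flare difference, balanced failures*
- Flares only: 16/64 = 25.0% versus 12/32 = 37.5%. Difference −12.5 points, p = 0.20, HR = ln(0.75)/ln(0.625) = 0.61.
- Add 8 and 4 failure-only patients (12.5% in each arm): 24/64 = 37.5% versus 16/32 = 50.0%. The difference is still −12.5 points, p = 0.24, but HR = ln(0.625)/ln(0.5) = 0.68, closer to 1.

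*Reversal.* Flares 20/64 versus 8/32 give +6.3 points, against active. Adding 4 and 8 failure-only patients gives 24/64 versus 16/32, −12.5 points. The failure-only difference is 6.3% − 25.0% = −18.8 points, which opposes and exceeds the +6.3.

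**The case against.** The best defence is that the composite is pre-specified and openly described. Section 7.2.14 and Table 5 give the event, its date, the single-count rule and the earlier-date rule. Treating failure as an unfavourable outcome matches the primary analysis and BICLA. Steroids or prohibited drugs may suppress or hide a flare, so a flare-only analysis that censors at failure risks informative censoring. Much of the decomposition is available elsewhere: flare proportion, failure proportion, time to failure and a by-patient listing. These are also secondary endpoints, and the superiority claim rests on SRI-4. All of this stands. It supports keeping the composite, but it does not justify a flare-only title or the absence of a counterpart matching Section 2.2.

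A reader might also infer more than the documents support:

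- **That a patient who tapers steroids after Day 150 is scored as flaring.** Section 7.1.1 lists, among conditions whose breach makes usage unallowable, "Between Day 150 and Day 210 (i.e., within 60 days of primary endpoint assessments), oral CS doses must be held constant". Section 7.2.14 and Table 5, however, refer to a prohibited medication or a burst, and date the event at a first dose. A reduction is neither and has no such date. The wording is ambiguous; it does not establish that result.
- **That the two analyses will point in opposite directions.** This requires failure-only differences that oppose and exceed the flare difference. It is possible but not expected.
- **That any particular loss or gain of power follows.** Such figures depend on assumed rates and on how far flare and failure overlap. Section 7.1.1 itself describes bursts given for increased lupus activity, so overlap is plausible.

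**Conclusion.** The point holds as a mismatch between the defined endpoint and its analysis. Section 2.2 and Section 7.2.5 concern BILAG flare; Section 7.2.14 and Table 5 analyse flare or medication failure under a flare title. A difference in medication use can therefore be reported as a flare effect, and balanced failures can pull the hazard ratio towards 1.

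The illustrations move p from 1.00 to 0.07 with no flare difference at all, but only to 0.35 when half of the failures occur in patients who flare anyway. They rest on assumed counts, chi-square tests in place of the log-rank, and full follow-up to Day 210. The primary endpoint is unaffected. The change should be made, because a secondary result would otherwise carry the wrong name.

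**What to change.** 1. Retitle Section 7.2.14 and Table 5 as time to first BILAG flare or medication failure.
2. Add a flare-only time-to-event analysis that matches Section 2.2 and Section 7.2.5, with a stated rule for medication failure: for example, treat it as a competing event, or continue follow-up for flare regardless of failure.
3. Tabulate the type of first event (flare or failure) by arm.
4. Reconcile the burst wording in Section 7.2.14 and Table 5 with the broader steroid-usage wording in Section 7.1.1, so that it is clear which failures count and how a failure without a first dose is dated.

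The cost is SAP wording and one or two extra outputs, with no new data. The flare-only analysis will have fewer events and so less precision, and its handling of failures needs an explicit assumption. That is a reason to report both analyses under accurate titles.

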**Table 5**

| Situation   | Date of Event or Censoring   | Outcome |
|--|---|----------------|
| Patient has a BILAG A Flare or >1 BILAG B Flare (Noted as BILAG 1A/2B Flare) prior to or on their Day 210 visit                  | Date of first BILAG 1A/2B Flare   | Event          |
| Patient is designated a medication failure (received prohibited meds or unallowable CS burst) prior to or on their Day 210 visit | Date of first dose of medication leading to medication failure designation. These dates will be obtained from date of the medication failure identified by the sponsor based on the prior and concomitant medication eCRF form. | Event          |
| Patient withdraws from study (no BILAG 1A/2B Flare, no medication failure) prior to or on their Day 210 visit                    | Censored at date of last non-missing BILAG flare assessment (prior to or on withdrawal) through Day 210   | Censored       |
| Patient completes the study (no BILAG 1A/2B Flare, no medication failure)  | Censored at date of last non-missing BILAG flare assessment through Day 210   | Censored       |
| Patient dies during study (no BILAG 1A/2B Flare, no medication failure) prior to or on their Day 210 visit                       | Censored at the day of death  | Censored       |

An event will be counted once in a patient who is a medication failure and also experiences a BILAG flare. Date of event will be the date of the earlier of the two reasons.

These analyses will also be performed for the MAD Phase 1b with the exception of the statistical testing.

Time to first BILAG A Flare or >1 BILAG B Flare data will be provided in a by-patient listing in the full analysis set.

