### 3.3. Sample Size Considerations

Sample size in the Phase 1b part of the study is based on operational consideration.

The sample size in the Phase 2 POC study is based on the primary endpoint, SRI-4 Response at Day 210. Based on efficacy data from a recently completed study with Ustekinumabiii, where the primary endpoint was also SRI-4, the sample size in the phase 2 part of the BOS161721-02 study is set at 96 evaluable patients. In the Ustekinumab study of 102 patients, a statistically significant difference in SRI-4 response was shown in favor of Ustekinumab (62% of Ustekinumab treated patients achieved SRI-4 response vs. 33% in patients receiving placebo). The Ustekinumab phase 2 study is an appropriate comparator to BOS161721-02 because both studies share the same primary endpoint of SRI-4 response and BOS161721 and Ustekinumab have overlapping mechanisms of action (T follicular helper and Th17 cell biology).

Sponsor: Boston Pharmaceuticals, Inc.  
Protocol Number: BOS161721-02  
SAP Version and Date: Version 4.0, 23Apr2021

Approximately 110 additional patients will be randomized in a 2:1 ratio to BOS161721 versus placebo to achieve approximately 96 evaluable patients in the FAS of the phase 2 portion. This assumes 14 patients will discontinue prior to having received treatment or having completed a post-baseline efficacy measure. Enrollment and randomization will be monitored in a blinded fashion and may be increased if needed to ensure at least 96 evaluable patients are randomized into the FAS (see Section 6.1).

A total of 96 evaluable patients randomized provides 80% power to detect a treatment difference of 29% in SRI-4 response rates at Day 210, based on a targeted 2-sided significance level of 10% and using a 2-sided Pearson's chi-squared test. This assumes a response rate of 62% for BOS161721 and 33% for placebo.

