## 6.2. Patient Disposition

Disposition data will be summarized for all randomized patients. The number of patients in each analysis set population, the number of patients who discontinued study treatment including reasons, and the number of patients who discontinued the study including reasons will be summarized. The number of patients who completed the study, duration on study treatment in days and duration on study in days will also be summarized. Data will be presented overall, by study phase, and treatment group.

A by-patient listing of patient disposition data including reason for discontinuation, if applicable, will be presented for all randomized patients. A by-patient listing of randomization details will also be provided for all randomized patients.

A by-patient listing of inclusion/exclusion criteria and screen failures will be produced for all enrolled patients. Screen failures will otherwise not be included in any analyses.

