**Table 2**

| Analysis   | Analysis Population | Criteria   |
|--|---------------------|--|
| Primary Analysis

LOCF for missing data,
Medication
Failures=Non-Responder | FAS                 | 
The primary analysis of the primary efficacy endpoint will be performed based on LOCF methods for missing data.
 
 
(1) Medication failures are considered non-responders on and after the date of medication failure
 
(2) Early withdrawals/discontinuations prior to study day 159 will be considered non-responders after the date of early withdrawal/discontinuation
 
 |

|  |     |  |
|--|-----|--|
|  |     | 
 
a. If patient is a medication failure prior to withdrawal/discontinuation, patient will be considered a non-responder on and after the date of medication failure.
 
b. In case of early withdrawal/discontinuation after study day 159 but before Day 210 such that patient has Day 180 data but is lacking Day 210 data in a patient without medication failure, the Day 180 data will be carried forward to Day 210.
 
 
(3) Patients with missing Day 180 and Day 210 data without prior medication failure and without early withdrawal/discontinuation prior to study day 159 are considered not evaluable and are excluded from analysis
  |

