**Table 4**

| Situation  | Date of Event or Censoring  | Outcome |
|---|--|----------------|
| Patient is designated a medication failure (received prohibited meds or unallowable CS burst) | Date of first dose of medication leading to medication failure designation. These dates will be identified by the sponsor based on the prior and concomitant medication eCRF form. | Event          |
| Patient withdraws from study (no medication failure)  | Censored at date of withdrawal   | Censored       |
| Patient completes the study (no medication failure)   | Censored at last study visit   | Censored       |
| Patient dies during study (no medication failure)   | Censored at the date of death  | Censored       |

Sponsor: Boston Pharmaceuticals, Inc.  
Protocol Number: BOS161721-02  
SAP Version and Date: Version 4.0, 23Apr2021

Kaplan-Meier curves of TTMF will be plotted over time.

These analyses will also be performed for the MAD Phase 1b with the exception of the statistical testing.

Time to medication failure data will be provided in a by-patient listing in the full analysis set.

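### Time to flare counts a medication failure as an event but censors withdrawal for unrecorded lupus worsening, with no supportive analysis, and dates deaths by a different rule from its other censoring rows

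*SAP*

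**What the plan says.** In SAP Version 4.0, Section 7.2.14 and Table 5 define time to first BILAG A flare or more than one BILAG B flare through Day 210.

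- **Events.** A qualifying BILAG flare on or before the Day 210 visit is an event. So is a medication failure in that period: "they will be considered as having a BILAG flare (event"), dated at the first dose of the offending drug.
- **Withdrawal from the study.** A patient with neither event is "Censored at date of last non-missing BILAG flare assessment (prior to or on withdrawal) through Day 210", whatever the reason for leaving.
- **Completion.** Also censored at the last non-missing flare assessment through Day 210.
- **Death.** "Censored at the day of death".

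The analysis is the one set out for time to medication failure (TTMF) in Section 7.2.12.2: Kaplan-Meier curves, a two-sided log-rank test and a Cox model with treatment as its only factor. For TTMF itself, Table 4 has withdrawals "Censored at date of withdrawal" and deaths censored at the date of death.

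The primary analysis handles exits differently (Section 7.1.1, Table 2): "Early withdrawals/discontinuations prior to study day 159 will be considered non-responders after the date of early withdrawal/discontinuation". On reasons for leaving, Section 6.2 says that "the number of patients who discontinued the study including reasons will be summarized", but it does not list the reason categories.

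**The concern.** Because a medication failure is deemed a flare whether or not BILAG shows one, the endpoint already accepts evidence of deterioration from outside BILAG. Take two patients who deteriorate in the same way and have no recorded BILAG 1A/2B flare. One starts a prohibited drug and is an event. The other withdraws first and is censored. The order of exit and first dose decides the outcome.

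The three methods assume that a censored patient had the same future risk as those who stayed. That is doubtful when the reason for leaving is lack of efficacy or worsening disease. If such exits are more frequent in one arm, the curves, the log-rank p-value and the hazard ratio can shift.

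The SAP tests its handling of exits elsewhere. The SRI-4 analysis has the alternatives in Table 2. PGA change has two approaches to medication failure and withdrawal (Section 7.2.6.2), which CLASI change also uses. BICLA, CLASI and SLEDAI-2K response each add Sensitivity Analysis 2. The two time-to-event endpoints have a single rule each. Section 4.1 says that the effect of premature withdrawal will be assessed, but gives no method.

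The death row is a separate matter that needs no assumption about why patients leave.

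**Working it through.** **1. The plan's own figure.** The SAP gives no event rate, hazard ratio, event count or power for either time-to-event endpoint. Its only sizing statement concerns SRI-4: "A total of 96 evaluable patients randomized provides 80% power to detect a treatment difference of 29% in SRI-4 response rates at Day 210", at two-sided 10%, 2:1, 62% against 33% (Section 3.3).

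With 32 placebo and 64 active patients, the pooled rate is (32 × 0.33 + 64 × 0.62)/96 = 0.523. The null SE is √[0.523 × 0.477 × (1/32 + 1/64)] = 0.1081. The alternative SE is √(0.33 × 0.67/32 + 0.62 × 0.38/64) = 0.1029. The continuity correction is 0.5 × (1/32 + 1/64) = 0.0234. Then z = (0.29 − 0.0234 − 1.645 × 0.1081)/0.1029 = 0.862, which is 80.6% power. The figure reproduces with the correction (86.2% without it). It does not bear on this point except by giving the planned arm sizes.

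**2. Who is affected.** Reading the rows of Table 5 together:

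| Patient with worsening lupus, on or before Day 210 | Outcome |
|---|---|
| Qualifying flare recorded at or before withdrawal | Event |
| Prohibited drug or unallowable corticosteroid use first, then withdrawal | Event |
| Withdrawal with no qualifying flare recorded (sub-threshold, or not assessed at exit) and no such drug | Censored |
| Death with neither event | Censored at day of death |

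Only the last two rows are at issue.

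**3. Illustration of size.** All rates here are assumed. Placebo risk by Day 210 is 40%. If a share of would-be events in each arm is censored just before it happens, then approximately

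observed HR ≈ true HR × (1 − share lost on active)/(1 − share lost on placebo).

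Two simulations were set against this formula. For a true HR of 0.65 (active risk 1 − 0.60^0.65 = 28%), the measure is an event-rate ratio per person-visit over seven monthly visits (6,400:3,200 patients, 50 repeats). For 0.60 and 1.0 it is a Cox fit to 150,000 patients, 2:1, with 10% background withdrawal.

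| True HR | Lost, placebo | Lost, active | Formula | Simulated |
|---|---|---|---|---|
| 0.65 | 30% | 10% | 0.65 × 0.9/0.7 = 0.84 | 0.82 |
| 0.65 | 10% | 30% | 0.65 × 0.7/0.9 = 0.51 | 0.51 |
| 0.65 | 20% | 20% | 0.65 | 0.65 |
| 0.60 | 30% | 10% | 0.77 | 0.77 |
| 0.60 | 20% | 10% | 0.68 | 0.66 |
| 0.60 | 10% | 20% | 0.53 | 0.54 |
| 0.60 | 10% | 30% | 0.47 | 0.47 |
| 0.60 | 10% or 20% | same | 0.60 | 0.59-0.60 |
| 1.0 | 30% | 10% | 1.29 | 1.27 |
| 1.0 | 10% | 30% | 0.78 | 0.77 |

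**4. The same at the planned size.** With 64 and 32 patients, the assumed risks give 64 × 0.28 = 17.9 and 32 × 0.40 = 12.8 events. Losing 10% and 30% of them means about 1.8 active and 3.8 placebo patients. SE(log HR) ≈ √(1/17.9 + 1/12.8) = 0.37, so a 90% interval around 0.65 runs from about 0.36 to 1.18. The shift to 0.82 is ln(0.82/0.65) = 0.23 on the log scale, or about 0.6 of a standard error.

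**5. Death row.** BILAG is not scored at death. Censoring on that day adds the time since the last assessment as flare-free, up to about 30 days if the monthly visits were kept.

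**The case against.** A reader might infer that anyone who leaves for worsening lupus is lost as an event. The documents do not support that. The withdrawal row covers only patients with no flare and no medication failure, and it uses assessments up to and including withdrawal. The SAP also refers to end-of-treatment and premature-discontinuation assessments, so many exits may have a BILAG. This part of the objection stands and limits the point to unrecorded or sub-threshold worsening.

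It is also tempting to say that any rescue treatment counts as a flare. It does not: only prohibited medication or unallowable corticosteroid use counts, and Section 7.1.1 allows one burst up to Day 120.

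Nor is bias demonstrated. Equal loss leaves the ratio unchanged, the unequal losses are assumed, and the resulting shifts lie well inside the interval that a trial of this size would give. That stands too. Imprecision does not remove a systematic shift, however, and a pre-specified supportive run would show whether the result depends on these few patients.

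TTMF might seem to share the flaw. There, medication failure is the endpoint itself. Censoring someone who never took the drug is the usual convention, and both of those Table 4 rows use the end of follow-up. The contrast with the primary endpoint is also only partial: the non-responder rule in Table 2 applies before study day 159, and later leavers with Day 180 data have it carried forward. A binary composite and a time-to-flare endpoint may treat exits differently without either being wrong.

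**Conclusion.** The point holds in limited form. Table 5 counts one route out of deteriorating disease as a flare and censors another, and no analysis checks whether that matters. The time-to-flare results may be biased in either direction if worsening-related exits without a recorded flare differ by arm. With an assumed 10% against 30% loss, a true ratio of 0.60-0.65 would appear as about 0.47-0.51 or 0.77-0.82. Smaller imbalances give smaller shifts, and equal loss gives practically none. The SAP offers no figure for these losses, so neither size nor direction can be predicted.

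The inconsistent censoring date for deaths is certain from the text. It is small, affecting only patients who die without an event by Day 210.

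A reader might conclude that death must become part of the main endpoint. The documents do not require that: it would change the question from flare to flare or death, which is a trade-off and not a correction. Both time-to-event endpoints are secondary and carry no multiplicity adjustment (Section 4.3), so the primary conclusion is unaffected.

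**What to change.** 1. In the death row of Table 5, censor at the last non-missing BILAG flare assessment on or before death and through Day 210, as in the withdrawal and completion rows.
2. Before unblinding, pre-specify one supportive analysis of time to flare. In it, death on or before Day 210 counts as an event at its date. So does study withdrawal in that period with a recorded reason of lack of efficacy or disease worsening, where the disposition form captures that reason. Label it as a broader endpoint and report its hazard ratio and log-rank p-value beside the main result.
3. The same run for TTMF is optional.

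Keep the main definitions of both endpoints. The cost is a few lines of SAP text and one extra run. Death dates are already used in Tables 4 and 5 and reasons for leaving are already summarised, but the reason categories need checking against the form. The downside is one more result to explain, on an endpoint wider than flare. Choosing it after unblinding would be data-driven, so it has to be fixed beforehand.
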